**A randomized controlled trial investigating the pediatric patient experience
of subantimicrobial dose doxycycline for acne treatment**

- Study protocol
- Statistical analysis plan
- Informed consent form

NCT number: NCT05399290

Date: October 8, 2022

Study Protocol

Inclusion criteria

Participants are eligible for inclusion in the study if they: are between ages 13 and 17, diagnosed with moderate to severe acne, did not have other skin conditions on their face, were not previously treated with antibiotics for acne nor received antibiotics for any reason within the last month, did not start a new prescription regimen for their acne within the last three months, did not obtain a positive pregnancy test in the clinic, and had no cognitive impairments. This minimizes confounding factors in treatment response and evaluation of acne (e.g., erythema from other skin conditions). 22 adolescents were identified as eligible and, with their parents, consented to participate in the study during the 11/20/2020 through 09/20/2021 study period. No changes to eligibility were made during the study period.

Randomization and Blinding

Once consent is obtained, eligible sample adolescents are randomized in a non-blinded, parallel fashion and in equal allocation to take either 20 mg or 100 mg doxycycline BID for 12 weeks. Additionally, the same over the counter regimen of Adapalene 0.1% gel and Benzoyl Peroxide 2-5% wash was prescribed.

Patients are randomized by choosing a folded piece of paper from a bag that determined their dose. No blinding to treatment arms occurred to mimic a real world where patients are informed of their dose. This allowed for the determination of patient-perceived effectiveness despite patient awareness of taking a lower dose.

Materials and methods

Participants are emailed a brief Qualtrics survey¹⁸ link on the day of enrollment and every two weeks thereafter to self-report their doxycycline dose and perceived facial acne severity using the validated *Patient-Centered Acne Severity Scale*¹⁹ containing a 10-point visual analog Likert-type scale. Each respondent is also invited to report any medication changes and submit open-ended comments concerning their use of doxycycline or their acne experiences. Those who submit at least three survey responses will be included in the analysis. After 12 weeks of treatment, participants complete a follow-up appointment at three months for clinical evaluation.

All participants are to be screened, enrolled, and treated through the Messenger Dermatology Clinic. Treatment is initiated at the same visit as enrollment and data collection ends at the three-month appointment. Patients picked up their prescription from the pharmacy of their choosing; the clinic and study personnel do not dispense the medication themselves. The Qualtrics software is programmed with a de-identified study identification number and message encryption.

Statistical Analysis Plan

Data analysis will be performed with *S.P.S.S. Version 28* analytic software using Friedman repeated measures test and Chi square test. For all analytic procedures, a two-tailed coefficient $\alpha < 0.05$ will be observed to indicate statistical significance.

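### Entry severity is mixed in an unstratified draw of 22 patients, and the SAP names no comparison of the doses that accounts for it; the loss is precision and accuracy given the draw, not overall alpha.

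*Combined protocol and SAP*

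**What the plan says.** Under Inclusion criteria, participants must be "diagnosed with moderate to severe acne". No quota is set for either grade, and the split is not given. The same section reports that "22 adolescents were identified as eligible and, with their parents, consented to participate in the study".

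Under Randomization and Blinding, patients are allotted "in equal allocation to take either 20 mg or 100 mg doxycycline BID for 12 weeks". The mechanism is a paper lot: "Patients are randomized by choosing a folded piece of paper from a bag that determined their dose". No stratification, blocking or minimization is described.

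Under Materials and methods, the outcome is self-rated facial acne severity on an instrument "containing a 10-point visual analog Likert-type scale", requested "on the day of enrollment and every two weeks thereafter".

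The Statistical Analysis Plan has the data analyzed "using Friedman repeated measures test and Chi square test", two-sided at 0.05. It names no covariate, no stratified test and no use of entry severity in comparing the doses.

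**The concern.** Severity at entry is likely to predict the later self-rating. With about 11 patients per arm, a simple draw will often put more severe patients in one arm. An unadjusted comparison carries that difference into the dose contrast, where it can add to a dose difference or mask one. Variation due to severity also stays in the error term of a very small trial.

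Eligibility is settled before the dose is drawn, so the diagnosis cannot be influenced by knowing the dose. That matters because the trial is not blinded and the outcome is self-rated. As planned, the diagnosis serves only to admit patients.

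**Working it through.** The documents give no power, SD, effect size or severity split, so there is no stated figure to reproduce.

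**Inputs from the documents:** 22 patients; equal allocation, taken as 11 per arm; a 10-point self-rating; Friedman and chi-square; two-sided 0.05.

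**Assumptions:** 11 of 22 severe (7 as an alternative); severe patients rate 2 points higher (range 1 to 3); within-grade SD 2.

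**1. Chance imbalance.** With 11 severe, the probability of k severe in one arm is C(11,k) × C(11,11−k) / C(22,11), and C(22,11) = 705,432.
- 6 v 5, either way: 2 × 462² / 705,432 = 0.605. A difference of 3 or more is therefore 1 − 0.605 = 0.395.
- 7 v 4, either way: 2 × 330² / 705,432 = 0.309.
- A difference of 5 or more: 0.395 − 0.309 = 0.086.
- With 7 severe, the probabilities for 3 or more and 5 or more are 0.361 and 0.063.

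**2. Shift in an unadjusted mean difference** = gap × (difference in severe patients) / 11.
- 7 v 4: 2 × 3/11 = 0.55 points (0.27 for a 1-point gap, 0.82 for 3).
- 8 v 3: 2 × 5/11 = 0.91 points.

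**3. False positives given the split.** Simulated two-sample t-test, no dose effect, 2-point gap.

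| Split | Unadjusted | Severity-adjusted |
|---|---|---|
| 7 v 4 | about 6% | about 5% |
| 8 v 3 | 12-13% | about 5% |

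**4. The named test that can compare arms.** Exact enumeration of an uncorrected 2×2 chi-square, 11 severe, no dose effect, with assumed response rates for moderate/severe patients.

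| Response rates | 3-patient imbalance | 5-patient imbalance |
|---|---|---|
| 60/40% | 5.6% | 7.0% |
| 70/30% | 6.4% | 12.2% |
| 80/20% | 7.1% | 21.2% |

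Averaged over all draws, the rate is 5.3-5.5% in these three settings.

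**5. Friedman.** On a simulated data set, adding a different constant to each patient's scores left the result unchanged (statistic 8.928, p = 0.178 both times). A stable difference in level drops out because scores are ranked within patient.

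**6. Precision.** With share severe q, gap g and within-grade SD s, severity accounts for q(1−q)g² / [q(1−q)g² + s²] of the variance. For q = 0.5, g = 2, s = 2 this is 1/(1+4) = 20%, a variance ratio of 1/0.8 = 1.25. That ratio ignores the degree of freedom spent and residual imbalance, so simulated power is the better guide. For a true 2-point dose difference, averaged over draws:

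| Severity gap | Unadjusted t-test | Regression with severity |
|---|---|---|
| 1 point | about 58% | about 58% |
| 2 points | about 51% | about 59% |

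If the arm with the 2-point benefit is also the one that drew more severe patients (2-point gap), power is 29% unadjusted and 57% adjusted at 7 v 4, and 17% and 51% at 8 v 3.

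**The case against.** **Friedman is not defeated by a level difference.** A reader might infer that neither named test can cope with mixed severity. For Friedman that is wrong, as step 5 shows. What it leaves in place is severity-dependent change: faster or slower improvement, regression to the mean, and floor or ceiling effects. These are not quantified here. Its larger limitation is that it tests change over time, not one dose against the other.

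**The t-test is not in the SAP.** This stands. Steps 2, 3 and 6 describe a between-arm comparison of scores that the plan does not contain. They show what such a comparison would lose if specified without severity. Step 4 covers the named test.

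**The worst figures belong to uncommon draws.** This also stands. The 39% covers differences of 3 or more, mostly 7 v 4, where false positives are about 6%. The 12-13% belongs to 8 v 3, and a split that extreme or worse occurs in only 6-9% of draws.

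**A separate grade may not exist.** The protocol gives one eligibility phrase and does not say that clinicians recorded moderate and severe separately. Its presence in the chart is an inference.

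**The enrolment-day self-rating is a finer covariate.** It is on the outcome scale, but the documents do not say whether it precedes the draw. Treatment starts at the enrolment visit and the same survey asks for the dose, so the rating may be given with the dose known. The eligibility diagnosis avoids that problem.

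**Conclusion.** The point holds as a gap in precision and in accuracy given the draw obtained. No planned comparison of the doses accounts for entry severity, and in 22 patients a noticeable imbalance is common (36-39% of draws for 3 or more severe patients, with 7 or 11 severe). At the usual size of imbalance, the harm is a shifted estimate and lost power; marked false-positive inflation needs the rarer 5-patient difference.

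A reader might infer that the missing stratification inflates the trial's type I error or invalidates the randomization. The documents do not support that: averaged over draws, alpha stays near 5%. Nor do they show that an imbalance occurred.

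The sizes rest on an assumed split, gap and SD, and on an 11/11 allocation. The protocol does not say whether papers were replaced after each draw. The three-response rule ("Those who submit at least three survey responses will be included in the analysis") could also reduce or unbalance the analyzed set. If severity is weakly prognostic, there is nothing to gain.

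**What to change.** Stratifying the draw is no longer possible: the stated study period ended on 09/20/2021 and the document is dated October 8, 2022. The remedy is in the analysis. Add to the SAP:

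> The arms as drawn are compared on the self-rated score with a regression model containing dose and the clinician's severity diagnosis (moderate or severe) made before the draw, taken from the enrolment-visit chart. The number of severe patients in each arm is reported.

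Use the grade only where the chart recorded it before the draw. Do not regrade patients afterwards with the dose known.

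Regression is preferred to a van Elteren stratified rank-sum test, which at a 1-point gap has about 52% power against 58% for the unadjusted t-test.

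The cost is SAP wording and one field abstracted from 22 charts. The model spends one degree of freedom, about 2 percentage points of power if severity is not prognostic, and it gains little if nearly all patients share one grade.

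### A fall in self-rated severity in the 20 mg arm reflects the whole regimen and cannot by itself show that the lower doxycycline dose is perceived as effective; the SAP names no comparison between doses

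*Combined protocol and SAP*

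**What the plan says.** The section Randomization and Blinding assigns patients "in equal allocation to take either 20 mg or 100 mg doxycycline BID for 12 weeks", so every patient takes doxycycline. It then adds: "Additionally, the same over the counter regimen of Adapalene 0.1% gel and Benzoyl Peroxide 2-5% wash was prescribed". The natural reading is that both arms receive these topicals.

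The same section explains the open-label design: "No blinding to treatment arms occurred to mimic a real world where patients are informed of their dose". The next sentence states what this achieves: "This allowed for the determination of patient-perceived effectiveness despite patient awareness of taking a lower dose".

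Under Materials and methods, patients self-report "perceived facial acne severity using the validated" scale named there, a 10-point rating, through a "survey¹⁸ link on the day of enrollment and every two weeks thereafter". Treatment starts at the enrollment visit. No arm on topicals alone and no run-in on topicals is described. Patients may also add free-text comments about doxycycline or their acne, but no analysis of these is described.

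The Statistical Analysis Plan says data will be analyzed "using Friedman repeated measures test and Chi square test", two-tailed at 0.05. It does not say which variable goes into which test, or whether Friedman is run within each arm or on all patients. It names no estimate of the difference between doses.

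**The concern.** The outcome rates the patient's face, not a drug. In the 20 mg arm three acne treatments start together, in patients who know what they are taking. Any fall in the rating combines the effect of doxycycline, the effect of two topicals, the natural course of the acne and expectation. Nothing in the plan separates these.

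The Friedman test asks whether ratings differ across time points in one set of patients. It makes no comparison between doses. If its result in the 20 mg arm were taken as the evidence on perceived effectiveness, the same result could arise with doxycycline contributing nothing.

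At stake is what the trial may conclude about the lower dose. The randomization does support a doxycycline-specific statement, namely how perceived severity differs between the two doses on a common background, but the SAP does not specify that comparison.

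**Working it through.** The documents give no effect size, variance, power or sample-size figure, so there is no stated number to reproduce. The point is settled by the design; the arithmetic only illustrates it.

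**Step 1: what each contrast contains.** Write the mean 12-week fall as

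- 20 mg arm: D20 + T + N + E20
- 100 mg arm: D100 + T + N + E100

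where D is doxycycline, T the topicals, N natural course and E expectation given the known dose. If the components add, the change within the 20 mg arm estimates the whole first line. The difference between arms is (D100 − D20) + (E100 − E20): T and N cancel. The shared topicals therefore do not bias the comparison between doses. That comparison still does not identify D20, because D20 = D100 = 0 and D20 = D100 = 1 give the same difference when expectation is the same in both arms.

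**Step 2: how readily a within-arm test is significant with no doxycycline effect.**

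- From the documents: enrollment plus every two weeks to week 12 gives 12/2 + 1 = 7 ratings; 22 patients in equal allocation gives 22/2 = 11 per arm. This is an upper limit, since patients with fewer than three survey responses are excluded.
- Assumed: score = round(6.5 − fall × t/6 + patient effect + error), limited to 1–10, t = 0 to 6. Patient SD = SD × √ρ and error SD = SD × √(1 − ρ), where ρ is the within-patient correlation. Doxycycline effect zero. Friedman p < 0.05, n = 11.

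For a 2-point fall from other causes:

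| SD | ρ | Error SD | Significant |
|---|---|---|---|
| 2.5 | 0.3 | 2.5 × √0.7 = 2.09 | about 39% |
| 2 | 0.5 | 2 × √0.5 = 1.41 | about 78% |
| 2 | 0.7 | 2 × √0.3 = 1.10 | about 96% |

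Friedman ranks within patient, so apart from rounding and the scale limits the result depends on the fall relative to the error SD. At SD 2 and ρ 0.5, falls of 0, 1, 2 and 3 points give about 4%, 23%, 78% and 99%. A separate simulation with patient SD 1.5 and error SD 1.0 gave 4.5%, 43%, 98% and 100% for the same falls. The percentages move with the assumptions; the attribution problem does not.

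**Step 3: what the between-dose comparison can say.** In that second simulation, with a common 2-point fall from other causes and a Mann-Whitney test on change from baseline:

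| Added by 20 mg | Added by 100 mg | Between-arm test significant |
|---|---|---|
| 0 | 0 | 4.65% |
| 1 | 1 | 4.5% |
| 0 | 1 | about 28% |

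The error rate is held, which confirms that the common background does no harm. A non-significant result is equally likely (about 95%) whether both doses do nothing or both work. It also occurs in 100 − 28 = 72% of trials where only 100 mg adds a point.

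**Step 4: precision.** By the normal approximation with 11 per arm, the standardized difference giving 80% power is (1.96 + 0.84) × √(2/11) = 2.80 × 0.426 = 1.19 SD. Power is about 47% at 0.8 SD and 22% at 0.5 SD. The 95% interval half-width is about 1.96 × 0.426 = 0.84 SD of the change score.

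**The case against.** **The sentence explains non-blinding.** It follows directly on the statement that patients know their dose. This stands. A reader might infer that the plan commits to reporting a significant fall in the 20 mg arm as doxycycline effectiveness. No section says so: the SAP gives two test names and a significance level, with no within-arm rule and no criterion for effectiveness. What remains is that the sentence says what the design can determine, and the only repeated-measures test named cannot deliver that for the lower dose.

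**A common background is ordinary add-on design.** This also stands. A reader might infer that the topicals confound the trial or should be removed. They do not confound the randomized comparison, and nothing here argues for changing the regimen.

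**The trial is about patient experience, not pharmacology.** If the aim is perceived response to the whole regimen, or a perceived difference between doses, the objection largely falls away. The text fits either reading but states neither, which is a reason to reword. The free-text comments are specific to doxycycline only in part, are optional and have no planned analysis.

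**Regression to the mean.** A reader might add this to the causes of a fall, since entry requires moderate to severe acne. Entry is by diagnosis, and no threshold on the self-rating scale is stated, so it is speculative and is not relied on.

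**The simulation builds in a fall and then finds it.** True. It shows how easily a fall from other causes reaches significance, not how large such a fall would be.

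**Conclusion.** The point holds as a limit on attribution and a gap in the planned analysis. A fall in the 20 mg arm, however significant, cannot by itself show that the 20 mg dose is perceived as effective. The between-dose comparison is the only doxycycline-specific contrast available, and the SAP does not specify it. Because patients know their dose, that contrast includes the effect of knowing it, which the protocol intends.

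The documents do not support the stronger conclusions that the randomized comparison is biased or that a false claim of effectiveness is already written into the plan.

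The conclusion rests on the design as described: doxycycline and the same topicals in both arms from enrollment, and no topical-only reference. The figure of about 39% to 96% for a within-arm Friedman test, with zero doxycycline effect and a 2-point fall from other causes, rests wholly on the assumed SD and correlation range.

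**What to change.** 1. In Randomization and Blinding, reword the sentence on patient-perceived effectiveness along these lines: *Change in perceived severity within an arm describes perceived response to the combined regimen of doxycycline, adapalene and benzoyl peroxide, and is not evidence that either doxycycline dose is effective.*
2. In the Statistical Analysis Plan, add a between-arm comparison of change in perceived severity from baseline, reported as an estimate with a 95% confidence interval, and name the time point. The document is dated October 8, 2022, after the stated study period ended on 09/20/2021, so the addition should carry its own date.
3. State that a non-significant difference between arms will not be reported as effectiveness or equivalence of the lower dose.

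Item 1 alone is not enough: it would leave the between-dose difference as the only doxycycline conclusion without an analysis to produce it. No arm, patient, visit or treatment changes. The cost is a narrower claim and, with 22 patients, a wide interval that may leave the dose question open.

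### The SAP plans no between-arm estimate or interval for the severity score, so neither a fall within the 20 mg arm nor a non-significant test can support a conclusion about the lower dose

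*Combined protocol and SAP*

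**What the plan says.** The protocol (Randomization and Blinding) describes an open-label, parallel-group trial with patients allocated "in equal allocation to take either 20 mg or 100 mg doxycycline BID for 12 weeks". Both arms are prescribed the same over-the-counter adapalene gel and benzoyl peroxide wash. The reason given for not blinding ends: "This allowed for the determination of patient-perceived effectiveness despite patient awareness of taking a lower dose".

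The size of the trial appears under Inclusion criteria as a count of those enrolled: "22 adolescents were identified as eligible and, with their parents, consented to participate in the study". No power, expected difference, SD or margin is given.

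Under Materials and methods, perceived severity is self-reported at enrollment and every two weeks on an instrument "containing a 10-point visual analog Likert-type scale". The analysis set is defined by response: "Those who submit at least three survey responses will be included in the analysis".

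The Statistical Analysis Plan is two sentences long. Analysis is to be done "using Friedman repeated measures test and Chi square test". One criterion covers everything: "For all analytic procedures, a two-tailed coefficient" below 0.05 "will be observed to indicate statistical significance". It specifies no effect estimate, no confidence interval and no rule for reading a non-significant result.

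**The concern.** A trial that randomizes patients to two doses can tell us about the lower one chiefly by comparing it with the higher one. Neither named test is tied to that comparison. The Friedman test asks whether scores change across time points within the same patients. The chi-square test could compare arms, but the SAP does not say on what variable.

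Two misreadings are therefore left open. First, a significant fall over time among 20 mg patients could be credited to low-dose doxycycline, although those patients also use two topical treatments and may improve for other reasons. Second, a non-significant arm comparison, whichever test is used, could be reported as similar perceived effectiveness when the trial was too small to tell. A threshold of p < 0.05 with no estimate or interval gives the reader no means of detecting either.

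**Working it through.** **Nothing to reproduce.** The plan has no sample-size or precision calculation. The figures below show how much 22 patients can say about a difference between arms.

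**Inputs from the documents**
- 22 consented, equal allocation: 22 / 2 = 11 per arm if exactly balanced.
- Two-sided alpha 0.05.
- A 10-point severity scale.
- Surveys at weeks 0, 2, ..., 12: 12 / 2 + 1 = 7 scheduled. Three responses suffice for inclusion, so an included patient may have no week-12 score.

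**Assumptions, because the documents give no figure**
- SD of 1.5, 2 or 2.5 points.
- 9 or 8 per arm as sensitivity cases for losses.
- An unadjusted two-sample t-test as a stand-in, since no between-arm test of the score is named.

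**Precision.** Half-width of the 95% CI = t(0.975, 2n − 2) × SD × sqrt(2/n). At n = 11 this is 2.086 × sqrt(2/11) × SD = 0.89 SD.

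| Per arm | In SD units | SD 1.5 | SD 2 | SD 2.5 |
|---|---|---|---|---|
| 11 | 0.89 | 1.3 | 1.8 | 2.2 |
| 9 | 1.00 | 1.5 | 2.0 | 2.5 |
| 8 | 1.07 | 1.6 | 2.1 | 2.7 |

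If the observed difference were exactly zero with SD 2 and 11 per arm, the interval would run from −1.8 to +1.8 points. It would leave open a disadvantage of the lower dose of up to 1.8 points.

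**Chance of a non-significant result.** This is 1 − power from the noncentral t distribution with 2n − 2 degrees of freedom and noncentrality (difference / SD) / sqrt(2/n).

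| True difference | 11 per arm | 9 per arm | 8 per arm |
|---|---|---|---|
| 0.5 SD | 80% | 83% | 85% |
| 0.8 SD | 57% | 64% | 68% |
| 1.0 SD | 39% | 49% | 54% |
| 1.25 SD | 20% | 30% | 36% |
| 1.5 SD | 8% | 15% | 20% |

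The chance crosses 50% at 0.88 SD with 11 per arm, 0.98 SD with 9 and 1.05 SD with 8. At SD 2 and 11 per arm, true differences of 1, 1.5, 2 and 3 points are non-significant 80%, 61%, 39% and 8% of the time.

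**If the chi-square test compares responders between arms.** Exact enumeration at 11 per arm, without continuity correction, gives power of 30% for 80% versus 50% responders and 50% for 80% versus 40%. These response rates are illustrative; the documents define no responder.

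**The case against.** **The aim may not be comparative.** A reader might infer that the trial sets out to show the two doses are perceived as similar, and that the plan therefore cannot answer its stated aim. The documents do not support that. The sentence on awareness of the lower dose explains why patients were not blinded. No passage speaks of non-inferiority, equivalence or similarity, and the question could be read as one about the 20 mg arm alone. This stands against the stronger claim. It does not rescue the analysis, because on the single-arm reading the shared topical regimen prevents a fall in score from being attributed to the dose.

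**Non-significance is not assured.** A reader might also infer that a non-significant result is likely even when the lower dose is clearly worse. The figures do not bear that out for large differences. At SD 2 and 11 per arm, a 2-point disadvantage is missed 39% of the time and a 3-point one 8%. The documents do not say how many points would count as clearly worse.

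**The figures are for a test the SAP does not name.** This is correct, and they are illustrative only. The SD and the losses are assumed, and a 10-point item is only roughly suited to a t-test. That a stand-in is needed reflects the gap itself: the plan has no between-arm analysis of the score to evaluate.

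**The risk arises from silence.** Also correct: nothing says that p > 0.05 will be read as similarity. The point is that the plan neither prevents that reading nor supplies the estimate that would correct it.

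**Conclusion.** The point holds in this form: the SAP specifies no between-arm estimate or interval for the severity score, so its planned output would not support a conclusion about the perceived effectiveness of the lower dose relative to the higher one. That follows from the text and needs no assumption.

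The size of the problem depends on the stand-in t-test and an exact 11/11 split. On that basis, non-significance is more likely than not for true differences below about 0.9 SD, and the interval extends about 0.89 SD either side of the estimate. Converting to points needs an assumed SD: 1.3 to 2.2 points over SD 1.5 to 2.5. Losses widen this, while baseline adjustment may narrow it. The finding is not that the trial fails a stated similarity objective, since it states none.

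**What to change.** Add to the SAP:

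> The between-arm difference in severity score at week 12 (20 mg minus 100 mg, as randomized), adjusted for the enrollment score, is estimated with its two-sided 95% CI from a repeated-measures model that uses all available two-weekly scores, so patients without a week-12 score still contribute. A rank-based interval (Hodges-Lehmann) for the change score is a sensitivity analysis. A non-significant difference is not interpreted as similar effectiveness, and the conclusion states the largest disadvantage of the lower dose that the CI does not exclude.

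The text should also name the covariance structure. Six post-enrollment time points give 6 × 7 / 2 = 21 parameters if it is left unstructured, which is too many for 22 patients. It should note that the model relies on missing scores being explained by the observed ones, and say what the chi-square test compares.

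Label the comparison exploratory and added after data collection. The document is dated October 8, 2022, and the stated study period ended on 09/20/2021. Even a patient enrolled on that last day would have completed 12 weeks (84 days) by 12/13/2021.

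The cost is a modest amount of extra analysis on data already collected. The interval makes the imprecision visible but does not remove it, and the result may have to be reported as inconclusive.

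### The three-survey rule selects randomized patients on surveys returned after randomization, so it can bias any arm comparison, and it secures neither a baseline nor a last score

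*Combined protocol and SAP*

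**What the plan says.** The protocol, Materials and methods, has participants emailed a survey "link on the day of enrollment and every two weeks thereafter to self-report their doxycycline dose and perceived facial acne severity". The analysis set is then fixed in one sentence: "Those who submit at least three survey responses will be included in the analysis". No survey week is named. The same part of the protocol says that "data collection ends at the three-month appointment"; that visit is described as a clinical evaluation, and nothing says that it supplies the survey score.

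Randomization and Blinding describes equal, open-label allocation for 12 weeks and gives the reason for not blinding: "This allowed for the determination of patient-perceived effectiveness despite patient awareness of taking a lower dose".

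The Statistical Analysis Plan says the data will be analysed "using Friedman repeated measures test and Chi square test", two-sided at 0.05. It names no all-randomized set, missing-data method, sensitivity analysis, time point or between-arm contrast.

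**The concern.** Randomization protects a comparison only for the patients who were randomized. Here a patient stays in the analysis by returning surveys. At most one qualifying survey belongs to the enrollment day, so inclusion always depends on at least two later responses. Those are given by adolescents who know their dose and who supply the outcome themselves. A patient who loses faith in the dose and stops answering after week 2 is removed altogether, although two scores are on file. Yet perceived effectiveness when the dose is known is what the protocol wants to learn.

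The rule also counts surveys without asking which ones. A patient with weeks 2, 4 and 6 is analysed with no baseline and no end score. A patient with only the enrollment and week-12 scores, the pair that most directly measures change, is left out.

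**Working it through.** The documents state no response rate, SD, effect size or power, so there is no plan figure to reproduce. From the documents: 22 consented, equal allocation (taken as 11 per arm), 12 weeks, a survey at enrollment and every two weeks. That gives 12/2 + 1 = 7 surveys if one is sent at week 12, and 6 if not; the documents do not say. All other inputs are assumptions.

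**1. What the rule admits.** With seven surveys, 35 + 35 + 21 + 7 + 1 = 99 response patterns have three or more answers. Of these, 42 lack the enrollment score, 42 lack week 12 and 16 lack both, so 99 − 42 − 42 + 16 = 31 have both. With six surveys, 42 patterns qualify, 16 lack the enrollment score, and nobody has a week-12 score.

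**2. Scattered non-response.** Each survey is returned independently with probability p. For K surveys, expected exclusions are 22 × P(Bin(K,p) ≤ 2). The share of included patients with both first and last scores is p² × [1 − (1 − p)^(K−2)] / P(Bin(K,p) ≥ 3).

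| p | Excluded of 22, K = 7 | First and last scores, K = 7 | Excluded of 22, K = 6 | First and last scores, K = 6 |
|---|---|---|---|---|
| 0.7 | 0.63 | 50% | 1.55 | 52% |
| 0.8 | 0.10 | 64% | 0.37 | 65% |
| 0.9 | 0.00 | 81% | 0.03 | 81% |

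**3. Patients who stop.** All answer at enrollment and a fraction h stops after each survey. A patient is excluded by stopping after the first or second survey, so the count is the same for six or seven surveys: 11 × [1 − (1 − h)²] = 1.07, 2.09, 3.05 of 11 at h = 0.05, 0.10, 0.15. The matching overall return rates over seven surveys are 86%, 75% and 65%.

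**4. Shift in the arm difference.** If 2 of 11 are excluded from one arm and none from the other, and their mean change is worse than that of the remaining 9 by a gap g, that arm's mean moves by g × 2/11. For g = 1, 2, 3 points this is 0.18, 0.36, 0.55. For scale, with a common SD of 2 the standard error is 2 × √(1/9 + 1/11) = 0.90, so the shift is 0.20, 0.40 or 0.61 SE. At g = 3 the ratio runs from 0.40 (SD 3) to 0.81 (SD 1.5).

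The shift is zero if exclusion is unrelated to outcome, or if the number excluded and their gap are the same in both arms. Equal counts alone do not suffice: one excluded per arm with opposite 3-point gaps gives 3/11 + 3/11 = 0.55.

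**5. Does the SAP repair it?** No. Friedman's test works within patients and does not compare arms. If run on all seven surveys it needs complete blocks: 22 × p⁷ = 1.8, 4.6, 10.5 patients at p = 0.7, 0.8, 0.9. The SAP does not say which surveys enter the test, or what the chi-square test compares.

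**6. What using every score recovers.** This is a simulation with no true arm difference: intercept SD 1.5, response SD 1.74, residual SD 0.7 (SD of 12-week change √(1.74² + 2 × 0.7²) = 2.0). The worst 2/11 of one arm give only weeks 0 and 2, and the enrollment mean is common to both arms. Entries are the spurious week-12 difference in points.

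| Stopping follows | Response | Three-or-more set | All scores, random intercept only | All scores, true covariance |
|---|---|---|---|---|
| true eventual change | reached by week 2 | 0.560 | 0.306 | 0.07 |
| true eventual change | half by week 2 | 0.557 | 0.433 | – |
| true eventual change | linear | 0.562 | 0.522 | – |
| true eventual change | late | 0.562 | 0.561 | – |
| observed early scores | reached by week 2 | 0.554 | 0.267 | 0.00 |
| observed early scores | half by week 2 | 0.468 | 0.288 | 0.00 |
| observed early scores | linear | 0.276 | 0.146 | 0.00 |
| observed early scores | late | 0.113 | 0.00 | 0.00 |

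(A dash means no figure is given.) When stopping depends only on scores already submitted, data are missing at random and a correct covariance removes essentially the whole shift. What a random intercept leaves in those rows is model misspecification. When stopping follows a response that has not yet appeared, the early scores carry no information about it and no covariance can recover it.

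**The case against.** The strongest reply is that the rule may exclude almost nobody. That stands for scattered non-response: at 70 to 90% return over seven surveys the expected loss is under one patient of 22. Material bias needs patients who stop early, for reasons tied to outcome, and differently by arm. The documents give no response counts, so this can be neither shown nor ruled out.

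A second reply is that missing scores stay missing under any analysis set. That is true, and step 6 shows recovery ranging from nothing to all of the shift. The replacement set, which requires one score, can also in principle select after randomization. But it drops only patients who supplied no outcome at all, and it reports them by arm.

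A third is that the missing between-arm contrast, the undefined chi-square test and Friedman's complete blocks are separate gaps in the SAP. They are; they are raised here only because they mean that the SAP does not cure the rule.

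A reader might infer that the trial's result is biased, or biased towards one dose. The documents do not support that: they give neither exclusions by arm nor how the excluded patients scored. A reader might also look for an upper limit on the bias. None can be set, because the number excluded and their gap are both unknown.

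**Conclusion.** The point holds as a possibility of bias and should be fixed. The rule selects dose-aware, self-rating randomized patients on survey return after randomization, and nothing elsewhere in the protocol or SAP offsets it. That it secures neither a baseline nor a last score follows from the text alone and needs no assumption.

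The sizes are illustrations resting on assumed response patterns, gaps and SDs, and on 11 per arm: exclusions from practically none to about 3 of 11 per arm, and a shift of 0.18 to 0.55 points for a net loss of two patients from one arm. Similar exclusion counts in the two arms would not by themselves show that the comparison is sound.

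A reader might take the enrollment score as a clean pre-treatment baseline with the same expected value in both arms. The documents do not secure this: randomization follows consent, treatment starts at the enrollment visit, and the enrollment-day survey already asks patients "to self-report their doxycycline dose and perceived facial acne severity". Dose awareness may have coloured that first score.

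**What to change.** Replace the inclusion sentence with:

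> All randomized participants with at least one severity score will be analysed in the arm to which they were allocated, regardless of self-reported dose, using every score submitted; participants with no score will be reported by arm.

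Add to the SAP:

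- **Estimate.** The between-arm difference at the last scheduled survey (state whether that is week 10 or week 12), from a repeated-measures mixed model with arm, categorical week, arm-by-week and small-sample degrees of freedom (Kenward-Roger or Satterthwaite).
- **Covariance.** One that lets patients differ in response over time, such as a random intercept and slope or another less restrictive structure the data support; not a random intercept alone.
- **Baseline.** Constrain the enrollment mean to be equal in both arms only if that score was given before the dose was known. Otherwise leave it free and state that it may reflect dose awareness.
- **Sensitivity and reporting.** Keep the three-or-more-response set and Friedman within arm, naming the surveys used, as sensitivity analyses. Report response counts and exclusions by arm.

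Participants "consented to participate in the study during the 11/20/2020 through 09/20/2021 study period". Twelve weeks after 09/20/2021 is 12/13/2021, before the document date of October 8, 2022, so outcomes may already have been seen. If they have been examined, label the change post hoc.

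The cost is one protocol sentence and one SAP paragraph, using scores already collected. The price is a model-based analysis of a 10-point scale, with wide intervals at 22 patients and limited ability to support a rich covariance. The change reduces the bias but may not remove it, both because missing-at-random may fail and because a simple covariance may be wrong. If stopping follows a true response that comes late, it recovers little or nothing.
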